## 11. Confidentiality

### 11.1. Patient confidentiality

Information on patients' identity shall be considered as confidential for all effects and purposes. Each site and patient will have a study code. Sites will be automatically coded in the study website through the identification code and password assigned to each investigator. Patients will be assigned a sequential number by the study website upon meeting all inclusion and no exclusion criteria. Confidential patient tracking sheets, listing patient sequential numbers together with patient name and date of birth, will be kept by investigators at the study site for identification.

Patients' identity should not be revealed nor published under any circumstances. Patient data recorded in the eCRF will be documented anonymously, coded with a patient number in such a way that only the investigator and site staff may associate particular data with an identified or identifiable individual or his/her medical record. All other parties involved in data management, analysis and storage will receive, and subsequently analyze, non-identifiable patient data.

### 11.2. Data confidentiality

By signing the investigator's confidentiality agreement, the investigator affirms to Takeda that information furnished by Takeda to the investigator will be kept in confidence and such information will be divulged to any expert committee, affiliated institution, and employees only under an appropriate understanding of confidentiality with such committee, affiliated institution and employees.

Data security will be maintained by data being recorded in a central database and tracked using an audit trail. The system will allow retrieving all entered data at any time, and will include security elements to prevent others than authorized staff from accessing data. Each user will have a specific profile which will limit his/her use of the database. A security copy of the database and the application files will be made outside the server housing the web-based study. Security copies will be periodically made and stored outside this server. A copy of the data stored in the database will be transferred to Takeda at the end of the study.

## 12. Study administration

The entire study will be managed by a project coordinator at the CRO who will coordinate the project and maintain fluid communication with the study sponsor and the study team at the CRO.

As part of the monitoring plan, regular phone calls (at least every two weeks) will be made by local study monitors in order to check inclusion status, resolve any issues, check data plausibility, etc.

## **13. Investigators compliance**

By signing the investigator's agreement, the investigator agrees to conduct the study in an efficient and diligent manner and in conformance with this protocol, generally accepted standards of good clinical practice and all applicable laws, rules and regulations relating to the conduct of the study.

The investigator shall prepare and maintain complete and accurate study documentation in compliance with applicable national and local laws, rules and regulations and, for each patient participating in the study, promptly record all data in the eCRF as required by this protocol.

## **14. Management and reporting of adverse events or adverse reactions**

### **14.1. Definitions**

#### **14.1.1. Definition of Adverse Event**

An AE is defined as any untoward medical occurrence in a patient administered a drug or has undergone procedures and which does not necessarily have a causal relationship with this treatment. An AE can therefore be any unintended sign (including an abnormal laboratory finding), symptom, or disease temporally associated with the use of a medicinal (investigational) product, whether or not related to the medicinal (investigational) product.

#### **14.1.2. Definition of Adverse Drug Reaction**

An Adverse Drug Reaction (ADR) is defined as 'Any noxious and unintended response associated with the use of a drug in humans, at any dose, where a causal relationship (drug-event) is at least a reasonable possibility'. x Adverse reactions may arise from use of the product within or outside the terms of the marketing authorization or from occupational exposure. Conditions of use outside the marketing authorization include off-label use, overdose, misuse, abuse and medication errors.

#### 14.1.3. Definition of Serious Adverse Event

An adverse event is considered “serious” if, in the view of either the investigator or Sponsor, it results in any of the following outcomes:

- Results in death
- Is life threatening (an adverse event is considered “life-threatening” if, in the view of either the investigator or Sponsor, its occurrence places the patient at immediate risk of death. It does not include an adverse event that, had it occurred in a more severe form, might have caused death)
- Results in persistent or significant disability/incapacity or substantial disruption of the ability to conduct normal life functions
- Results in congenital anomaly, or birth defect
- Requires inpatient hospitalization or leads to prolongation of existing hospitalization (hospitalization for treatment/observation/examination caused by AE is to be considered as serious)
- Other medically important events (Including transmission of an infectious agent)

Medical and scientific judgment should be exercised in deciding whether other situations should be considered serious, such as important medical events that may not be immediately life-threatening or result in death or hospitalization but may jeopardize the patient or may require intervention to prevent one of the other outcomes listed in the definition above. These events, including those that may result in disability/incapacity, should also usually be considered serious. Examples of such events are intensive treatment in an emergency room or at home for allergic bronchospasm; blood dyscrasias or convulsions that do not result in hospitalization; or development of drug dependency or drug abuse.

#### 14.1.4. Special Situations

The following special situations, although not necessarily considered to be AEs or ADR must be reported in the same way as ADR, or even in the same way as SAEs.

- Off-label use: situations where a medicinal product is intentionally used for a medical purpose not in accordance with the authorized product information.
- Overdose (accidental or intentional): administration of a quantity of a medicinal product given per administration or cumulatively which is above

the maximum recommended dose according to the authorized product information.

- Misuse of a medicinal product: situations where the medicinal product is intentionally and inappropriately used not in accordance with the authorized product information.
- Abuse of a medicinal product: persistent or sporadic, intentional excessive use of medicinal products which is accompanied by harmful physical or psychological effects.
- Drug exposure during pregnancy and/or breast-feeding. Exposure during pregnancy is considered either through maternal exposure or via semen following paternal exposure.
- Lack of efficacy/effectiveness
- Medication errors: are broadly defined as any error in the prescribing, dispensing, or administration of a drug, irrespective of whether such errors lead to adverse consequences or not.
- Occupational exposure: this refers to the exposure to a medicinal product, as a result of one's occupation, such as nurses who may handle products routinely in their occupational setting
- Falsified product: this refers to the use of a fake or counterfeit medicine, that passes itself off as a real, authorized medicine

#### 14.1.5. Criteria for Causal Relationship to the (Study) Drug

The following definitions of Related should be used to characterize the suspected causality of an AE. This assessment should be based on the Investigator's consideration of all available information about the event, including temporal relationship to drug administration, recognized association with drug product/class, pharmacological plausibility, and alternative etiology (eg, underlying illness, concurrent conditions, concomitant treatments):

- **Related:** There is a reasonable possibility that the drug caused the event. There is a reasonable temporal relationship between the drug administration and the event, and no other obvious alternative explanation for the occurrence of the event.
- **Not related:** There is not a reasonable possibility that the drug caused the event. There is evidence for (an) alternative explanation(s) for the event (eg, the event is explained by one or more of the following: a) the subject's medical condition (medical history, disease progress, indication), b) a concomitant medication for

which the event is labelled, or c) AE occurrence prior to the introduction of the medicinal product.

The investigator must make an assessment of causality using the above definition. Causality cannot be assumed in the absence of the investigator's assessment.

## **14.2. Handling of Adverse Events**

### **14.2.1. Reporting of Adverse Reactions**

According to the Order SAS/3470/2009, of 16 December, with published guidelines on post-authorization studies of drugs for human use, those studies in which it is not possible or not appropriate to do an individual assessment of the causal relation between clinical events and drugs of interest, individual reporting of suspected adverse reactions is not required. Studies labelled PAS-OD fall into this category and they do not require expedited reporting of suspected adverse reactions, unless otherwise specified by the AEMPS at the time of registration of the study.

In addition to that specified in the preceding paragraph, any relevant safety problem found during the course of the study will be made known to the AEMPS and the competent bodies of the Autonomous Communities involved, regardless of study design and documentation.

However, it is the responsibility of the investigator to report suspected serious adverse reactions that are detected during the course of the study to the contact point designated by the competent body on pharmacovigilance of the autonomous community in which the investigator reporting the case operates.

### **14.2.2. Collection and Recording of Adverse Events**

Collection and recording of AEs will commence after the patient has provided informed consent.

Information on all AEs or special situations, associated with the use of any product marketed by Takeda, whether initial or follow-up, serious or non-serious, that come to the attention of the investigator during the study visit should be recorded on the Takeda AE reporting form (see APPENDIX 5) and notified to the Sponsor within 24 hours of the Investigator's first awareness, using the following email address: [[contact]](mailto:[contact])

In case the CRO is aware of any AE or special situation associated with the use of any product marketed by Takeda, it shall be the responsibility of the CRO to send such information recorded on the Takeda AE reporting form (see APPENDIX 5) to the pharmacovigilance department at Takeda within 24 hours from reception through the email address [[contact]](mailto:[contact])

On a quarterly basis Takeda Pharmacovigilance will send a list of the adverse events received to the CRO in order to perform the corresponding reconciliation process. Then the CRO will send back the discrepancies to Takeda Pharmacovigilance for resolution.

2. INTRODUCTION

This statistical analysis plan (SAP) describes the planned analysis for VERNE study. In it is described all consideration over study data and are defined the tables, figures and listing (TLFs) that will be presented as result of the study.

Additionally includes definition of the different population and missing data consideration.

The statistical analysis plan will be signed and per protocol dataset will be defined before database lock.

Table of abbreviations

CD	Crohn's Disease
UC	Ulcerative Colitis
IBD	Inflammatory Bowel Disease
HBI	Harvey-Bradshaw Index
PMS	Partial Mayo Score
PNR	Primary non-response
LOR	Secondary Loss of response
PR	Partial response
SE	Side Effects
95% CI	95% Confidence Interval

3. SYNOPSIS

3.1. Study title

"Impact of co-morbidities on treatment response in inflammatory bowel disease: VERNE study"

3.2. Study Code

MACS-2015-101162

3.4. Design

A retrospective, non-interventional, multicentre, observational study that will include consecutive patients diagnosed with Ulcerative Colitis (UC) or Crohn's Disease (CD) who started treatment with biologics between June 2011 and June 2013.

3.5. Objectives

Primary:

- Evaluate the impact of the co-morbidities profile in IBD patients on treatment response to biological therapy.

Secondary:

- Evaluate the impact of extraintestinal manifestations profile in IBD patients on treatment response to biological therapy.
- Describe the percentage of IBD patients exhibiting co-morbidities.
- Determine the co-morbidities profile according to the level of IBD severity.

3.6. Total number of subjects

The present study will include patients diagnosed with UC or CD that started biological treatment between June 2011 and June 2013, attending physician gastroenterology services in Spain. In order to avoid a biased sample, investigators will recruit consecutive patients. It is estimated that a period of 4 months will be necessary to achieve the desired sample of 200 UC and 200 CD patients.

3.7. Inclusion Criteria

- Adult patients (aged ≥ 18).
- Patients diagnosed with UC or CD according to the "World Gastroenterology Organization Practice Guidelines for the Diagnosis and Management of IBD in 2010".
- Patients naïve to biologics that started treatment with biologics between June 2011 and June 2013.
- Patients in whose biological treatment was prescribed according to daily clinical practice.
- Patients that gave written informed consent.

3.8. Exclusion Criteria

- Patients that were participating in a clinical trial during the study reference period.
- Patients that, according to investigator's criteria is not capable to understand and fill in the study questionnaires or to give written informed consent.

3.9. Study treatment

The patients participating in this retrospective, non-interventional, multicentre, observational study will not receive treatment in relation to the study aside from the treatment already prescribed by their usual physician. In order to fulfill current legislations regarding non-interventional studies, investigators will commit to follow usual clinical practice.

4. STUDY POPULATIONS

4.1. Definition of study populations to analyse

Study Population: All patients who meet the selection criteria and have given their informed consent will be included in the analysis.

4.2. Disposition of subjects

A flowchart will be provided to describe the total included patients in each part of analysis for patients with Crohn's Disease and Ulcerative Colitis separately. Discrepancies between the numbers of patients of each part of the analysis will be described by number of patient, site and the reason of the discrepancy.

4.3. Study Discontinuations

Not applicable.

5. SUBJECT DESCRIPTION

5.1. Demographic and baseline description. General considerations

All analysis will be described for patients with Crohn's Disease and Ulcerative Colitis separately.

The demographic and baseline description will be performed for all "analyzed patients".

Given the descriptive nature of the study, the statistical methodology used will be based primarily on an exploratory analysis of the data through the calculation of descriptive parameters.

The continuous variables will be summarized in a table showing the mean, median, standard deviation and maximum-minimum range and the categorical variables will be presented as absolute frequencies and percentages.

5.2. Subject Characteristics

The analysis of continuous variables will be described by the mean, median, standard deviation, minimum and maximum. This analysis included the age of patients and number pack-year in smoking habits.

The analysis of categorical variables will be described by the distribution of frequencies and percentages.

This analysis included the following variables:

- Gender.
- Race (caucasian, asiatic, latin, black, other).
- Level of education (uneducated, primary education, secondary education, university education).
- Working status (student, self-employed, employed by other, retired, housework, unemployed, temporarily unable to work, permanently unable to work, other).
- Smoking habits (non-smoker, ex-smoker and smoker).
- Alcohol abuse (yes/no).

5.3. Disease characteristics

The analysis of continuous variables included the following variables:

- Time from diagnostic of disease (UC or CD) (time in months from the date of diagnostic until the date of informed consent).
- Charlson index.

The analysis of categorical variables included the following variables:

- Disease location (L1=terminal ileum; L2= colon; L3=ileum and colon; L4=upper gastrointestinal track; E1=proctitis; E2=left colitis; E3=extensive colitis).
- Disease behavior (only for CD patients) (B1=inflammatory; B2=stenosis; B3= fistulizing; B1p; B2p; B3p (p=perineal)).
- Extraintestinal manifestations:
 - Arthropathy and arthritis (yes/no).
 - Metabolic bone disease (yes/no).
 - Eye disease (yes/no).
 - Oral, aural and nasal disease (yes/no).

- Skin disease (yes/no).
- Hepato-pancreato-biliary disease (yes/no).
- Neurological disease (yes/no).
- Cardiovascular manifestations of IBD (yes/no).
- Pulmonary manifestations of IBD (yes/no).

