#### **6.3.2. Inclusion criteria**

- Adult patients (aged  $\geq 18$ )
- Patients diagnosed with UC or CD according to the "World Gastroenterology Organization Practice Guidelines for the Diagnosis and Management of IBD in 2010"
- Patients naive to biologics that started treatment with biologics between June 2011 and June 2013
- Patients in whose biological treatment was prescribed according to daily clinical practice.
- Patients that gave written informed consent

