#### 6.4.4. Study variables

The following **sociodemographic variables** will be collected from patients' medical records or directly from patients during the study visit, straight after their inclusion in the study:

- Age
- Gender
- Race (caucasian, asiatic, latin, black, other)
- Level of education (uneducated, primary education, secondary education, university education)
- Working status (student, self-employed, employed by other, retired, housework, unemployed, temporarily unable to work, permanently unable to work, other)
- Smoking habits (non-smoker, ex-smoker, smoker, number of cigarettes per day)
- Alcohol intake (units per week).

The following **clinical variables** will be collected from patients' medical records (when available) or directly from patients during the study visit, straight after their inclusion in the study:

- Date of diagnosis (UD or CD).
- Disease activity at the beginning of the reference period and at the study visit through collection of the following variables:
  - For UC patients:
    - Partial Mayo Score (PMS) (9 point scale that excludes the endoscopic appearance of the mucosa)
    - General disease activity:
      - Mild: up to four bloody stools daily and no systemic toxicity
      - Moderate: four to six bloody stools daily and minimal toxicity
      - Severe: more than six bloody stools daily and signs of toxicity, such as fever, tachycardia, anaemia, raised erythrocyte sedimentation rate.
      - Fulminant: More than ten bloody stools daily, continuous bleeding, anaemia requiring blood transfusion, abdominal tenderness and colonic dilatation on plain abdominal radiographs.
    - Disease anatomic extent: proctitis, left-sided colitis or pancolitis.
    - Endoscopy findings:

- Normal or inactive disease
- Mild disease (erythema, decreased vascular pattern, mild friability)
- Moderate disease (marked erythema, lack of vascular pattern, friability erosions)
- Severe disease (spontaneous bleeding, ulceration).
- For CD patients:
  - Harvey-Bradshaw Index (HBI) (a simplified version of CDAI)
  - General disease activity:
    - Mild to moderate: ambulatory patients able to tolerate oral alimentation without manifestations of dehydration, toxicity, abdominal tenderness, painful mass, obstruction or >10% weight loss.

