7.2. Primary efficacy endpoint

- **Primary endpoint:** Evaluate the impact of the co-morbidities profile in IBD patients on treatment response to biological therapy.

The analysis that will be performed to answer the objective will be the following:

In order to determine the level of correlation between the co-morbidities profile and treatment response, adjusting for sociodemographic and clinical profile of patients, two logistic regression models will be conducted. The dependent variable of the models will be the **lack of response during the induction phase and the loss of response during the maintenance phase**. In both models independent variables will include all comorbidities, as well as sociodemographic and clinical variables as covariates.

- The following potential variables will be considered for the analysis:
 - Crohn's Disease or Ulcerative Colitis.
 - Myocardial Infarction (yes/no).
 - Congestive Heart Failure (yes/no).
 - Peripheral Vascular Disease (yes/no).
 - Cerebrovascular Disease (yes/no).
 - Dementia (yes/no).
 - Chronic Obstructive Pulmonary Disease (yes/no).
 - Connective Tissue Disease (yes/no).
 - Peptic Ulcer Disease (yes/no).
 - Mild Chronic Hepatopathy (yes/no).
 - Diabetes Mellitus (yes/no).
 - Hemiplegic (yes/no).
 - Moderate-Severe Chronic Kidney Disease (yes/no).
 - Diabetes with lesions in target organs (yes/no).
 - Solid Tumor (yes/no).
 - Leukemia (yes/no).
 - Lymphoma (yes/no).

- Moderate-Severe Chronic Hepatopathy (yes/no).
 - Solid tumor with metastases (yes/no)
 - Acquired immunodeficiency syndrome (AIDS) (yes/no).
 - Gender.
 - Race (caucasian, asiatic, latin, black, other).
 - Level of education (uneducated, primary education, secondary education, university education).
 - Working status (student, self-employed, employed by other, retired, housework, unemployed, temporarily unable to work, permanently unable to work, other).
 - Smoking habits (non-smoker, ex-smoker and smoker).
 - Alcohol abuse (yes/no).
 - Time from diagnostic of disease.
 - Disease location.
 - Discontinuation the biological treatment (yes/no)
- Each one of the variables will be compared between the subjects with primary non-response vs primary response and primary response maintenance vs loss of response and those variables whose p-value is lower than 0.1 are considered potential variables for performing a logistic regression analysis.

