APPENDIX 1: INDEX OF SECTION 14 FOR THE CLINICAL REPORT

The following proposal for section 14 is done according to the pre-defined ICH-format. Minor changes from this planned index do not need to be amended in the SAP.

Comments in **Italics** will not be printed in table headers or footers.

Formal organization of tabulations may be changed during programming if appropriate, e.g., tables for the different variables may be combined into a single table, or tables with more than one variable may be split into several tables.

	TITLE	TABLE TYPE	ANALYSIS SET	COMMENT
14.	TABLES, FIGURES AND GRAPHS REFERRED TO BUT NOT INCLUDED IN THE TEXT			
14.1	DEMOGRAPHIC AND BASELINE DATA			
14.1.1	Subject disposition	CAT2	General population	
14.1.2	Subject characteristics			
14.1.2.1	Gender, Race	CAT2	Study population	
14.1.2.2	Level of education	CAT2	Study population	
14.1.2.3	Working status	CAT2	Study population	
14.1.2.4	Smoking habits / Alcohol abuse	CAT2	Study population	
14.1.3	Disease characteristics			
14.1.3.1	Time from diagnostic of disease	CONT2	Study population	
14.1.3.2	Charlson index	CONT2	Study population	

TITLE		TABLE TYPE	ANALYSIS SET	COMMENT
14.1.3.3 Disease location		CAT2	Study population	
14.1.3.4 Disease behavior		CAT2	Study population	
14.1.3.5 Extraintestinal manifestations		CAT2	Study population	

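### SAP 5.3 ends disease duration at informed consent rather than at the start of the first biologic, so the baseline value includes the whole interval from treatment start to consent.

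*SAP*

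**What the plan says.** SAP 5.3 lists among the continuous disease characteristics "Time from diagnostic of disease (UC or CD) (time in months from the date of diagnostic until the date of informed consent"). It follows the section titled "Demographic and baseline description. General considerations", and Appendix 1 assigns it Table 14.1.3.1 under "DEMOGRAPHIC AND BASELINE DATA".

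SAP 7.2 lists "Time from diagnostic of disease" among the potential variables for the primary analysis without redefining it, so the 5.3 definition carries over. It can reach both models: "In both models independent variables will include all comorbidities, as well as sociodemographic and clinical variables as covariates". Entry is conditional, since "those variables whose p-value is lower than 0.1 are considered potential variables for performing a logistic regression analysis", and stepwise selection follows.

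Treatment start is fixed by Protocol 6.3.2: "Patients naive to biologics that started treatment with biologics between June 2011 and June 2013". Under Protocol 6.1 the reference period runs from that start. Under Protocol 6.3.5 and 6.4.1 there is a single study visit, and consent is given before data collection begins. SAP 7.1 judges primary non-response at 10 weeks after start and loss of response at 6 months or later, with no upper limit. Protocol 6.4.4 collects both the date of diagnosis and the starting date of each biologic. Neither document defines disease duration at treatment start.

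**The concern.** In a prospective trial, consent and first dose nearly coincide, so ending disease duration at consent does little harm. Here they are years apart. Other baseline information is tied to treatment start: Protocol 6.4.4 takes disease activity at the beginning of the reference period, and SAP 7.3 classifies severity at baseline. Disease duration departs from that anchor.

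Two things are at stake.

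- **Baseline description.** A reader of Table 14.1.3.1 would take the figure as how long patients had had IBD when first treated, and it would be too long for everyone. Protocol section 4 discusses early introduction of biologics, and the planned table would hide who was treated early.
- **Meaning of the coefficient.** In the week-10 model the covariate contains time that had not yet elapsed when the outcome was read. In the loss-of-response model, patients who started earlier receive both a longer recorded duration and more opportunity to lose response.

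**Working it through.** **The plan's own figure.** Protocol 7.1 uses 10 events per variable, at most 10 variables and 50% non-response: 10 × 10 / 0.50 = 200 per disease. This is reproduced and does not depend on the definition of disease duration.

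**Inputs for the check.** Start window June 2011 to June 2013 (Protocol 6.3.2); four-month inclusion period (Protocol 6.3.1); outcomes at 10 weeks and at 6 months or later (SAP 7.1). The consent date is an assumption. The protocol's reference list contains a 2016 publication, so January 2016 is the main scenario, with earlier and later ones alongside.

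**Step 1: time added.** Recorded duration = (start − diagnosis) + (consent − start). The second term is the excess. For consent on 1 January 2016 it is 30.1 months (start 30 June 2013) to 55.0 months (start 1 June 2011). The table covers whole four-month windows. The later columns subtract 70/30.4375 = 2.3 months and 6 months.

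| Assumed consent window | Start to consent (months) | After week 10 | After month 6 |
|---|---|---|---|
| Jan–Apr 2015 | 18.1–46.9 | 15.8–44.6 | 12.1–40.9 |
| Jan–Apr 2016 | 30.1–59.0 | 27.8–56.7 | 24.1–53.0 |
| Sep–Dec 2016 | 38.1–67.0 | 35.8–64.7 | 32.1–61.0 |
| Sep–Dec 2017 | 50.1–79.0 | 47.8–76.7 | 44.1–73.0 |

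Example: a patient diagnosed in January 2013 and treated in March 2013 has a duration of 2 months at start. With consent in January 2016 the recorded value is 36 months.

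**Step 2: how much of the excess differs between patients.** With starts uniform over 25 months and consent uniform over 4 months, SD = √((25² + 4²)/12) = √53.4 = 7.3 months. Reliability = SD²/(SD² + 53.4). If the true duration SD is 48 months, this is 2304/2357.4 = 0.977; if 96 months, 9216/9269.4 = 0.994. Both SDs are assumptions. Most of the excess is a common shift, which moves the reported mean and median but largely goes into the intercept of a regression.

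**Step 3: effect on the duration odds ratio.** A simulation of 400,000 patients used gamma-distributed true duration (mean 84 months, SD 36 or 84), start-to-consent time of 30–55 plus 0–4 months, and a true log effect of 0 or −0.3 per 60 months. For loss of response, a hazard of 0.13 per year accrued up to consent. All of these are assumptions. Entries are odds ratios per 60 months, first with duration to biologic start, then with duration to consent.

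| Outcome | True effect | SD 36 | SD 84 |
|---|---|---|---|
| Fixed time (as at week 10) | none | 0.999 → 0.999 | 0.998 → 0.998 |
| Fixed time | −0.3 | 0.738 → 0.746 | 0.741 → 0.744 |
| Accrues with follow-up | none | 1.007 → 1.076 | 1.000 → 1.012 |
| Accrues with follow-up | −0.3 | 0.684 → 0.746 | 0.695 → 0.711 |

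As ratios, the fixed-time odds ratio moves by at most 0.746/0.738, about 1%. The accruing one moves by about 1% (1.012/1.000) to 9% (0.746/0.684). Duration is the only covariate in these models, so they say nothing about comorbidity odds ratios.

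**The case against.** The strongest reply is that duration is only an adjuster. The primary objective concerns comorbidities, the variable must pass a p < 0.1 screen and stepwise selection before it enters either model, and its own coefficient barely moves for week-10 non-response. All of that stands. A reader might infer that the comorbidity results are biased; neither the documents nor the calculation shows this.

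A reader might also infer that both models adjust for time after the outcome. That is firm only at week 10. Activity indices are collected at treatment start and at the study visit, so where loss of response is judged at the visit the covariate runs up to the outcome, not past it. It still contains all the time since start.

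Nor does the definition make duration at first treatment unobtainable: both dates are collected, and the plan simply does not use them together.

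The size depends on an undocumented consent date. Reference 33 is a 2010 guideline in the inclusion criteria but a 2016 consensus in the reference list, so that entry may have been updated, and 2016 need not date the first consent. This stands, and it is why a range is given.

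The SAP states its end date openly, so a footnote would prevent misreading. It would not supply duration at treatment start.

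It is tempting to extend the point to working status, because sociodemographic data "will be collected from patients' medical records or directly from patients during the study visit, straight after their inclusion in the study". The documents do not say to which date that item refers. Age is not among the SAP 7.2 candidates.

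**Conclusion.** The definition does not give duration at time zero, and nothing elsewhere in the protocol or SAP corrects it. The firm consequence is descriptive. Recorded duration exceeds duration at first treatment by about 30 to 55 months if consent was on 1 January 2016, by about 18 to 47 months if it fell in January to April 2015, and by more if later. These sizes rest on assumed consent dates; the direction does not.

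If the variable is selected, its odds ratio for primary non-response is little affected, because the added time is nearly the same for everyone. For loss of response the bias is small to modest: about 1% if true durations are widely spread (SD 84 months, null effect), up to about 9% if they are narrow (SD 36 months), assuming that loss accrues with follow-up. The main harm is to the baseline table and to the interpretation of the duration coefficient. The correction should be made because it is nearly free, not because the primary comparison is shown to be compromised.

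**What to change.** In SAP 5.3, define the variable as months from the date of diagnosis to the starting date of the first biologic. State in SAP 7.2 that the candidate variable uses this definition, and label Table 14.1.3.1 to match.

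The cost is one line of wording and one changed derivation from two dates that the protocol already collects. No new data are needed and the sample size stays at 200 + 200.

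This does not by itself adjust for unequal follow-up in the loss-of-response model. If that matters to the sponsor, it needs its own treatment, through a separate term for time from start to assessment or a time-to-event analysis. That is a separate decision.
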